#### 2.3. Sample size

#### 2.3.1.Pilot trial sample size

From each cluster a non-probability sample of 40 consecutive patient participants (320 in total) will be recruited. A formal power calculation is not required for a feasibility study as testing intervention effectiveness is not the aim. However, the sample size should be sufficient to estimate the uncertain critical parameters: Standard Deviation (SD) of the primary outcome, recruitment/consent rates, ICC and the average cluster size needed to inform the design of the future full-scale c-RCT with sufficient precision. A minimum of 8 clusters in total is needed to best estimate the ICC [2]. Using Swiger's formula for the variance of the ICC [3], the precision gain of the ICC estimate diminishes after 30-50 patients per cluster. As more clusters with fewer patients is preferred, an average of 40 patients from each cluster will be recruited, leading to a total sample of 320 patients. Allowing for a median consent rate of 70% [4], a total of 457 patients will be approached to participate, approximately 57-58 per cluster. This sample size will be efficient to estimate the feasibility outcomes.

On average, each cluster will have 5-10 cardiologists, who will see about 400-1000 patients per year. Approximately 30,500 patients per year have planned CA for stable angina. There are 98 UK NHS cardiac centres that perform CA. This suggests, on average, 312 patients are eligible per cluster. Accounting for a median consent rate of 70% [4], 218 patients could be consented in one year. Therefore, 40 patients per cluster within 12 months should be feasible.

#### 2.3.2. Full trial sample size

For the anticipated primary clinical outcome (Decisional Conflict Scale) at follow up, the ICC for patients treated within the same site will be estimated using a marginal or random effects model.

At present, we have no valid or reliable estimates for the critical parameters for the sample size calculation for the future c-RCT (hence the need for this feasibility study). However, assuming an ICC of 0.05 [5] and an effect size of 0.3-0.4 for the anticipated primary outcome [6,7], preliminary estimates suggest the full c-RCT with 90% power, significance level of 5% (two-sided) and allowing for variable cluster size, between 24 to 42 clusters would be needed, with an average cluster size of 40 patients per year, equating to 914 to 1618 patients in total.

#### 2.4. Framework

This study will use a precision framework.

#### 2.5. Statistical Interim analyses and stopping guidance

This study has no planned interim analysis or early stopping.

#### 2.6. Timing of final analysis

Analysis will be conducted when all data is in house and has been checked.

#### 2.7. Outcomes

2.7.1.Feasibility outcomes See section 1.2

2.7.2.Clinical outcomes

The patient questionnaires:

- The Decisional Conflict Scale
- Angioplasty Knowledge questionnaire
- Preparation for Decision-Making Scale (10-item version)
- Perceived Involvement in Care Scale

## 2.7.3. Overview of feasibility study uncertainties and outcomes

### Table 1: Overview of feasibility study uncertainties and outcomes

Uncertainty	Outcomes
Feasibility of cluster recruitment and their willingness to participate	
 
Number of Cardiology Departments approached, the number of responses to the 'Expression of Interest', and the number willing to participate.
 
Recruitment rate (Number of Cardiology Centres recruited in 4 months).
 

Feasibility of patient participant recruitment and retention	
 
Number of eligible patient participants, approached, consented, and recruited.
 
Recruitment rate (Number of patients recruited per month, per site).
 
Retention rate, defined as the proportion completing the anticipated primary outcome questionnaires (Decisional Conflict Scale questionnaire at T2).
 
Attrition (loss of participants who were assigned to intervention or control).
 
Rates of MACE and hospital readmission within 30-days of discharge.
 

Diversity and inclusivity of sample	
 
Characteristics of Cardiology Departments: geographical location, Index of Multiple Deprivation (IMD), size of cardiology workforce, presence or absence of on-site surgical cover, annual volume of planned angio/coronary angioplasty procedures.
 
Patient participant demographics: age, gender, ethnicity, level of social support, health and E-literacy, cardiac diagnosis, co-morbidities.
 
Number of non-English speaking participants requiring interpreter services (verbal and/or translation of documents).
 
Number of participants without access to digital technology (including smartphones, tablets, laptops, and the internet).
 

Characteristics and appropriateness of questionnaires as outcome measures in the future c-RCT	
 
Response rate (Number of participants who completed and returned the questionnaires divided by number of participants in the sample).
 
Item response rate (Number of valid responses divided by total number of responses requested).
 

Intra-cluster Correlation Coefficient (ICC) and sample size calculation for full scale c-RCT	
 
Estimate of the ICC of the Decisional Conflict Scale at T2 using a marginal or random effects model.
 
The full c-RCT sample size will be calculated based on estimates of the effect size (alongside previous research), the standard deviation and the ICC from the anticipated primary outcome analysis.
 

Practicality of implementing CONNECT in NHS settings	
 
CONNECT implementation:         
 
Number of participants who access CONNECT.
 
Percentage of pre-assessment clinic visits in which the CONNECT summary was used during the consultation.
 
Qualitative analysis of training session minutes and interview transcripts to summarise:                 
 
Potential variations in usual-care patient pathway for planned coronary angioplasty.
 
Practicalities of providing a digital PtDA in the NHS.
 
Barriers and enablers to integrating the CONNECT summary.
 
 
 

Reasons for non- consent to study participation	Qualitative analysis to summarise: • Reasons for Cardiology Departments nonparticipation. • Reasons for patient nonparticipation.

Uncertainty	Outcomes
Acceptability of	Qualitative analysis of interviews to explore:
CONNECT and study procedures	
 
Self-reported adherence to CONNECT and how it was used by patients at home and during the pre-assessment clinic.
 

	
 
Barriers and enablers to recruitment and using CONNECT at home and during pre-assessment clinic.
 

	
 
Understanding, appropriateness, and potential burden of questionnaire completion.
 

#### 2.7.4. Data collected and timing of outcomes

Measures	Enrolment	Baseline (T1)	Post Pre- Assessment (T2)
Brief Health Literacy Screening Tool (Chew et al 2004)	Х		
eHealth Literacy Scale (Norman & Skinner 2006)	X		
Decisional Conflict Scale (O'Connor, A. 2010)		Х	Х
Coronary Angioplasty Knowledge questionnaire. (Researcher Team generated)		Х	Х
Preparation for Decision-Making Scale (Bennett et al. 2010)			Х
Perceived Involvement in Care Scale (Lerman et al. 1990)			Х

**Enrolment**: After informed consent for study participation.

**Baseline**: Before using CONNECT at least 1 week before Pre-Assessment Clinic.

**Post Pre-Assessment Clinic**: After pre-assessment, but before coronary angio/angioplasty procedure.

Data collected:

**Study logs:** Patient identification Log, Screening Log, Enrolment/Withdrawal Log, and Pre-Assessment Log.

**Participant demographic and clinical details:** age, sex, ethnicity, live alone, employment status, internet access, scheduled procedure and treatment received, MACE, 30-day readmission after procedure, CAD presentation, CV history, smoking status, presence of comorbidities.

Health literacy questionnaires (n=2): BRIEF 3-item health literacy tool, 8-item eHealth Literacy Scale.

**Timepoint 1 patient reported questionnaires (n=2):** 9-item knowledge questionnaire, 10-item decisional conflict scale.

**Timepoint 2 patient reported questionnaires (n=4):** Repeated knowledge questionnaire with 4 extra questions about access to information and CONNECT, repeated 10-item decisional conflict scale, 10-item preparation for decision making scale, 13-item perceived involvement in care scale.

**CONNECT use:** Google analytics data.

## 3. Statistical Principles

#### 3.1. Confidence intervals and P-values

As the trial is a pragmatic parallel group RCT data will be reported and presented according to the CONSORT 2010 statement [8] and the CONSORT extension for pilot and feasibility studies [9]. As a pilot/feasibility study the main analysis will be mainly descriptive and focus on confidence interval estimation and not formal hypothesis testing. Results will be presented with their associated 95% confidence intervals. As this is a feasibility study and it's not powered to detect differences, P- values will not be used.

No methods for multiplicity adjustment will be used in this study.

#### 3.2. Adherence and Protocol Deviations

Adherence to CONNECT will be defined as: The percentage of patient participants in the intervention arm who report being able to successfully access CONNECT. This will be determined from the preassessment clinic study log.

A further secondary adherence measure will be the percentage of patient participants who take the personal summary to the pre-assessment consultation. We will present appropriate summary statistics for the rate of adherence in the intervention arm.

In addition, there will be google analytics data which will also be analysed to help determine adherence. This data will include:

- Number of visits to the website (in total or for a particular month/ period of time).
- Average time spent on the website.
- Average time spent on different sections of the website.
- The most viewed parts of the website.
- The section of the website where people leave (customer journey end).

#### 3.3. Analysis populations

The Intention To Treat (ITT) population includes all patients for whom consent is obtained and who are randomised to treatment. This is the primary analysis set and endpoints will be summarised for the ITT population unless stated otherwise.

The Per Protocol (PP) population includes all patients who accessed CONNECT on the treatment arm. This is a secondary analysis set.

#### 3.4. Withdrawal/Follow up

As a study progresses there may be a change in participants preferred level of participation. A participant may decide that they no longer wish to contribute with the study and cease involvement in any ongoing data collection. Participants may also be withdrawn from the study by the research or clinical care team due to clinical deterioration (e.g., hospitalisation). In these scenarios, data that has already been collected before change of status/withdrawal will be analysed unless participants specifically ask for it to be deleted. Any change of status/withdrawal will be recorded (date of withdrawal, reason and type of withdrawal) in the site Case Report Form and the Chief Investigator informed. As this is a feasibility study, participants who have a change of status/or are withdrawn will not be replaced. The number and percentage of patients withdrawing will be reported (as a proportion of all patients withdraw) by randomised group.

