4.3 Patient Participants (Nested Qualitative Study)

From the 240 patient participants recruited to the intervention arm of the main feasibility study, we will recruit a sub-sample of up to 40 patient participants (6-7 from each Cardiology Centre). Eligible patients will be those who are participating in the feasibility study and have not withdrawn from the study.

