#### 1.1. Background and rationale

Patient Decision Aids (PtDAs) are evidence-based interventions known to be effective in improving the quality of shared decision-making.

The CONNECT feasibility study is a cluster randomised controlled feasibility study with an embedded qualitative study. Eight clusters (NHS Trusts providing planned coronary angioplasty in England) will be recruited and randomised to the control or intervention arm at a 1:3 allocation ratio. Six clusters will implement a digital Patient Decision Aid 'CONNECT' and two clusters will provide usual care only. Questionnaires will be administered before and after delivery of intervention or control.

The overarching aim of this study is to determine whether it is feasible to conduct a cluster Randomised Controlled Trial (c-RCT) to test the effectiveness of CONNECT for improving shared decision-making for patients with stable angina.

The quantitative and qualitative data collected will enable us to assess:

- 1) the feasibility of delivering CONNECT in the planned coronary angioplasty patient pathway;
- 2) explore the acceptability of CONNECT to patients and cardiology teams;
- 3) assess the feasibility and acceptability of trial procedures.

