## 2. Study Methods

#### 2.1. Trial design

This is a two group, unblinded, multi centre, parallel cluster randomised controlled feasibility study with an embedded qualitative study. Clusters will be NHS Trusts that provide planned coronary angioplasty treatment for adults. Eight clusters will be recruited and randomised to the control or intervention arm at a 1:3 allocation ratio. Participants (n=320; 40 per cluster) will be patients with stable angina who are on the waiting list for planned coronary angioplasty or planned diagnostic coronary angiography with the potential to proceed immediately to treatment with coronary angioplasty ("angio query proceed"). Participants recruited from clusters in the intervention arm will receive the digital PtDA 'CONNECT'. Participants recruited from clusters in the control arm will

receive usual care. Questionnaires will be administered before and after delivery of intervention or control.

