#### 2.2. Randomisation

The eight Cardiology Departments are the units of analysis and will be randomised using stratified block randomisation with an allocation ratio of 3:1 to the intervention group and block size of four. Cardiology Departments will be stratified as appropriate, by factors such as the presence, or absence, of on-site surgical provision.

There will be no blinding, as the intervention will be delivered by the research nurse and cardiology teams. Randomisation will be conducted by the study statistician [name] and the statistician will conduct the randomisation blinded.

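### SAP 3.4 gives withdrawal by arm as a share of all withdrawals, so under 3:1 allocation equal withdrawal rates would be reported as 75% and 25% (minor denominator correction)

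*SAP*

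**What the plan says.** SAP 3.4 (Withdrawal/Follow up) ends with the reporting rule: "The number and percentage of patients withdrawing will be reported (as a proportion of all patients withdraw) by randomised group". The wording is ungrammatical, but the only denominator it names is the patients who withdrew.

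No other section supplies a different denominator for withdrawal:

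- Protocol 8.2.8, the matching section, describes how withdrawals are recorded but has no reporting rule.
- SAP Table 1 (section 2.7.3) lists "Attrition (loss of participants who were assigned to intervention or control") as a feasibility outcome, with no denominator.
- The same table lists "Retention rate, defined as the proportion completing the anticipated primary outcome questionnaires (Decisional Conflict Scale questionnaire at T2"), which is a separate measure.
- SAP 3.3 makes the intention-to-treat population the default for summaries, but only where nothing else is stated. Section 3.4 does state something else.
- SAP 4.2 gives complete-data counts by treatment group. These concern questionnaires, not withdrawal.

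The arms are deliberately unequal. SAP 2.2 has departments "randomised using stratified block randomisation with an allocation ratio of 3:1 to the intervention group and block size of four", and SAP 1.1 says "Six clusters will implement a digital Patient Decision Aid 'CONNECT' and two clusters will provide usual care only".

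**The concern.** A reader of a withdrawal table by arm expects to learn how likely a participant in each arm was to withdraw. A share of withdrawals does not answer that. It mixes the withdrawal rate with the size of the arm, and here one arm is planned to be three times the other. Under this rule the intervention arm will usually show the larger percentage simply because it is larger, and a real excess in the control arm can be hidden.

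What is at stake is a descriptive figure. After the progression table, SAP 4.1.1 says that attrition and retention rates are part of the information used to judge whether the full trial is feasible. A share of withdrawals is not an attrition rate. A statistician who followed section 3.4 to the letter would produce a percentage that cannot serve that purpose and that could be misread as differential dropout.

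**Working it through.** **Inputs**

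- Clusters per arm: 6 intervention and 2 control (SAP 1.1).
- Participants per cluster: 40 (SAP 2.1: "Participants (n=320; 40 per cluster) will be patients with stable angina").
- Withdrawal rates: none is given in either document. The rates below are assumptions.

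**Reproducing the plan's arm sizes**

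- Intervention: 6 × 40 = 240. This matches Protocol 4.3: "From the 240 patient participants recruited to the intervention arm of the main feasibility study".
- Control: 2 × 40 = 80.
- Total: 240 + 80 = 320, as stated.

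**Formulas**

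Let wI and wC be the withdrawal rates in the intervention and control arms.

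- Figure under SAP 3.4, intervention: 240·wI / (240·wI + 80·wC). The control figure is the complement.
- Withdrawal rate in an arm: withdrawals in that arm / participants enrolled in that arm.

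**Equal rates.** If wI = wC, the rate cancels and the intervention figure is 240/320 = 75%, whatever the rate.

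**Numerical cases (assumed rates)**

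| Rate, intervention | Rate, control | Withdrawals | Figures under SAP 3.4 |
|---|---|---|---|
| 5% | 5% | 12 and 4 | 75% and 25% |
| 10% | 10% | 24 and 8 | 75% and 25% |
| 20% | 20% | 48 and 16 | 75% and 25% |
| 10% | 20% | 24 and 16 | 60% and 40% |
| 10% | 30% | 24 and 24 | 50% and 50% |

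In the fourth row the control rate is double, yet the intervention figure is larger. In the fifth row a threefold difference disappears. In general the intervention figure is the larger whenever 240·wI > 80·wC, that is, whenever the control rate is less than three times the intervention rate.

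**With each arm's enrolled participants as denominator.** At 10% in both arms, 24/240 = 10% and 8/80 = 10%. In the fourth row, 24/240 = 10% and 16/80 = 20%. Both are shown correctly.

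**Using the whole sample would not repair it.** At 10% in both arms, 24/320 = 7.5% and 8/320 = 2.5%, still a threefold gap. The denominator has to be specific to the arm.

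**The case against.** The strongest reply is that this is a slip of the pen. The main clause, a number and percentage withdrawing by group, reads naturally as an ordinary rate, and the parenthesis is garbled. That may well be so. But the parenthesis is the only denominator the plan gives for withdrawal, so it should be corrected before analysis.

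The second reply is that nothing is lost. The same sentence promises the number withdrawing by arm, and the numbers recruited and the baseline tables by group supply the arm sizes, so any reader can work out the rates. This stands. It limits the harm, although it does not make the stated percentage right.

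Three stronger readings are tempting, and the documents do not support them:

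- *A reader might infer that the progression decision is affected.* The retention criterion in SAP 4.1.1 is the percentage of the whole patient sample completing the study. The section 3.4 percentage enters no Go, Amber or Stop threshold. Its link to feasibility is only the general remark on attrition and retention rates after the table.
- *A reader might infer that the report would show CONNECT causing dropout, or leave full-trial attrition impossible to plan.* The analysis is descriptive and without P-values (SAP 3.1), no rule draws a conclusion about CONNECT from withdrawal by arm, and the counts remain available. A possible misreading is as far as the text goes.
- *A reader might infer that attrition by arm, as a percentage, is itself a named outcome.* SAP Table 1 refers to participants assigned to either arm but specifies neither separate reporting nor a percentage.

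**Conclusion.** The point holds as a minor correction. As written, SAP 3.4 yields each arm's share of withdrawals and not its withdrawal rate.

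The 75% against 25% result under equal withdrawal does not depend on the assumed rate. It does depend on the planned 240:80 split. Forty per site is an average target, and if enrolment differs, the equal-rate figures become each arm's share of actual enrolment. The 60/40 and 50/50 examples depend wholly on the illustrative rates.

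No model, effect estimate, sample-size input or progression threshold changes.

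**What to change.** In SAP 3.4, replace the parenthesis with: *as a proportion of all participants enrolled in that randomised group, and overall*. Reasons and types of withdrawal, which are already recorded, may still be tabulated out of all withdrawals if that table is labelled as such.

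The cost is one phrase, with no new data and no change to any analysis. A confidence interval adjusted for site is not needed for this correction. With only two control clusters it would be very imprecise, and it would be a separate decision.

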#### 3.5. Baseline patient characteristics

The baseline demographics and clinical characteristics of the patients will be reported. For the continuous variables (e.g. age) either mean and SD will be presented or median and inter quartile range (IQR) depending on the distribution of the data. The number of observations used in each calculation will be presented alongside the summaries.

All baseline summaries will be presented in appropriate tabular form.

Data will be collected on the following: age, sex, ethnicity, health and digital literacy level, live alone, employment status, internet access, CAD presentation, CV history, smoking status, and presence of comorbidities.

## 4. Analysis

#### 4.1. Analysis methods

As this is a feasibility study the main analysis will be predominantly descriptive and focus on confidence interval estimations rather than formal hypothesis testing. The baseline demographics and clinical characteristics of the patients will be reported overall and by randomised group. For the continuous variables (e.g., age) either mean and SD will be presented or median and inter quartile range (IQR) depending on the distribution of the data. The number of observations used in each calculation will be presented alongside the summaries.

We will look at differences between groups for the anticipated primary outcome (Decisional Conflict Scale). A random effects model (or another appropriate method) will be used to estimate the difference between the two treatment groups adjusting for age, sex, health literacy score, living alone, health burden (number of co-morbidities) and baseline decisional conflict scale score as fixed effects and hospital as a random effect to account for clustering. This difference and its associated 95% confidence interval will be used to check that the likely effect is within a clinically relevant range (as confirmation that it is worth progressing with the full trial) and to inform the sample size calculation for the definitive study as outlined previously. Similar analyses will be conducted for other secondary endpoints.

For the anticipated primary outcome (Decisional Conflict Scale) at follow up, the ICC for patients treated with the same site will be estimated using a marginal or random effects model.

The mean/median for anticipated primary and secondary outcomes (e.g. Coronary Angioplasty Knowledge questionnaire) at baseline and post-pre-assessment (along with its variability) will be reported for all participants.

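### The 95% CI for the CONNECT effect rests on eight clusters (6 v 2) with no small-sample rule and an open choice of method; left uncorrected, the named model could cover about 87-92%

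*SAP*

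**What the plan says.** SAP 1.1 gives the allocation: "Six clusters will implement a digital Patient Decision Aid 'CONNECT' and two clusters will provide usual care only". SAP 2.1 gives the size: "Participants (n=320; 40 per cluster) will be patients with stable angina".

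For the anticipated primary outcome, SAP 4.1 says: "A random effects model (or another appropriate method) will be used to estimate the difference between the two treatment groups". The model has six patient-level covariates, including the baseline score, and "hospital as a random effect to account for clustering". SAP 3.1 adds: "Results will be presented with their associated 95% confidence intervals". P-values are excluded there, and SAP 2.4 adopts a precision framework.

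SAP 4.1 gives the interval two uses: to check that the likely effect is clinically relevant, as support for going on to the full trial, and to inform that trial's sample size. Secondary endpoints are to be analysed similarly. SAP 4.1.1 plans no sensitivity analyses. SAP 4.5 names R but no routine. Protocol 12.2 leaves the detail of the analysis to the SAP.

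Neither document says whether REML or ML is used, how degrees of freedom are set, whether standard errors are corrected for few clusters, or when the alternative method would replace the random effects model.

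**The concern.** The arm effect is estimated from differences between clusters. With eight clusters and two arms, about 6 degrees of freedom are available to estimate its error, and only two clusters inform the control side. A random effects interval built with a normal multiplier treats the between-cluster variance as well estimated, and at this size it is not. ML makes matters worse by biasing that variance downwards. Uncorrected sandwich standard errors are worse still.

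Without P-values, the interval carries the inference about effect. If it is too narrow, CONNECT's effect looks better determined than the design allows, at the point where the SAP consults it on progression and sample size. The open clause also lets the method be chosen after results are seen, and no sensitivity analysis would expose the difference.

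**Working it through.** **Inputs.** Clusters 6 v 2 (SAP 1.1); 40 patients per cluster (SAP 2.1); ICC 0.05 and effect 0.3-0.4 SD (SAP 2.3.2); 80% retention, the green threshold in SAP 4.1.1, giving 0.80 × 40 = 32 per cluster. The SD is set to 1.

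**The plan's own figure first.** The documents state no precision for the eight-cluster interval. The nearest figure is the full-trial size in SAP 2.3.2: 24 to 42 clusters, 914 to 1618 patients. Exact t calculations at 90% power and two-sided 5% give 265 patients in total (effect 0.4) and 469 (effect 0.3) before clustering. The coefficient of variation of cluster size is not stated; assuming 0.5, the design effect is 1 + ((0.5² + 1) × 40 − 1) × 0.05 = 3.45.

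- 265 × 3.45 = 914; 914 / 40 = 22.9, or 24 clusters in equal arms.
- 469 × 3.45 = 1618; 1618 / 40 = 40.5, or 42 clusters in equal arms.

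The SAP's figures reproduce, so the same ICC is used below.

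**Standard error of the arm difference, variance known, 40 per cluster.**

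- Variance of a cluster mean: 0.05 + 0.95/40 = 0.07375.
- SE = √(0.07375 × (1/6 + 1/2)) = √0.04917 = 0.222 SD.
- Half-width with 1.960: 0.43 SD. With t on 8 − 2 = 6 df (2.447): 0.54 SD.
- Ratio: 2.447 / 1.960 = 1.248, about 25% wider.
- Analytic check: a 1.96 multiplier applied to a t statistic on 6 df covers 90.2%.

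**Simulated coverage of a nominal 95% interval at ICC 0.05.** 4,000 trials per setting, 6 v 2 clusters, normal outcome, no covariates or stratification; Monte Carlo standard error about 0.3-0.7 points.

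| Interval | 40 per cluster | 32 per cluster | 20-60 per cluster |
|---|---|---|---|
| REML, 1.96 | 90.3% | 91.7% | 90.8% |
| ML, 1.96 | 86.7% | 88.3% | 87.0% |
| Marginal model, uncorrected sandwich, 1.96 | 75.9% | 78.1% | 76.7% |
| Marginal model, bias-corrected sandwich, t on 6 df | 93.1% | 93.6% | 94.0% |
| REML, t on 6 df | 95.9% | 96.1% | 95.2% |
| Cluster means, t on 6 df | 94.9% | 95.2% | 95.2% |

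A larger simulation (40,000 trials, equal cluster sizes of 32-40) gave 91%, 87-88% and 77% for the three uncorrected intervals, and 95% for REML with Satterthwaite degrees of freedom. Mean half-widths at ICC 0.05 were 0.42-0.44 SD for REML with 1.96 and 0.52-0.55 SD for the REML and cluster-mean intervals on 6 df.

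**Sensitivity to the ICC.** Over ICC 0.01-0.20, coverage was 90-94% for REML with 1.96, 85-93% for ML with 1.96 and 75-78% for the uncorrected sandwich. At ICC 0.01, REML with 1.96 reached 93-94%.

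**Zero variance estimates.** At ICC 0.05 the between-cluster variance is estimated as zero in about 7-11% of trials. In those trials, switching to a cluster-level t interval covered about 74-78%, against 73-77% for ignoring clustering. With equal clusters, a zero estimate arises when the between-cluster mean square is unusually small, and the cluster-level interval uses that same mean square. Keeping the REML standard error with t on 6 df covered 83-87% in those trials and 96% overall.

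**The case against.** The strongest reply is that the SAP is silent on the multiplier rather than committed to 1.96. A statistician could fit this model in R with Satterthwaite or Kenward-Roger degrees of freedom and comply fully. That stands: a reader might infer that the reported intervals will cover only 77-91%, but the documents support only that they could under-cover. The 77% end is further removed, because SAP 4.1 names a marginal model for the ICC only; for the effect it enters solely through the open clause.

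The stakes can also be overstated. The primary objective is feasibility (SAP 1.2), the study is not powered for the future primary outcome (protocol 1.3.2), and the stop/go table in SAP 4.1.1 has no row for the effect. SAP 4.1 sets no numerical range for clinical relevance, so no defined decision reverses. Half-widths of 0.43 and 0.54 SD both exceed the planning effect of 0.3-0.4 SD, so either interval says little about clinical relevance. All this lowers the severity. It does not remove the point, because SAP 4.1 still gives the interval a role in progression and sample size.

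Two wording points might be read as evidence of a wrong model. SAP 2.2 says "The eight Cardiology Departments are the units of analysis", yet the model is at patient level. SAP 2.1 says "Clusters will be NHS Trusts that provide planned coronary angioplasty treatment for adults", while the random effect is the hospital. The first reads as a slip for units of randomisation. On the second, the documents use hospital, site, department and Trust interchangeably, and nothing shows a cluster containing several hospitals. Neither demonstrates under-coverage.

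Finally, 2.447 is not the one correct multiplier: it assumes equal clusters and no cluster-level covariates. Adding a site-level stratum term would leave 5 df.

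**Conclusion.** The point holds as a gap in specification with a measurable consequence. If the random effects model in SAP 4.1 is reported with an uncorrected interval, a nominal 95% CI could cover about 87-92% at the SAP's own ICC of 0.05. The open clause would also admit a method covering about 77%. Standard small-sample intervals bring coverage to about 95-96%.

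These figures assume a normal outcome, 32-40 patients per cluster on average, and no covariates or stratification. The shortfall for REML is small if the ICC is near 0.01. The documents do not establish that the intervals will be too narrow, that the stop/go decision depends on them, or that the random effect is mis-specified. This should be fixed before analysis; it does not threaten the study's feasibility objectives.

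**What to change.** In SAP 4.1, delete the bracketed alternative and fix one method in advance:

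- a REML mixed model with the randomised cluster as the random effect and a small-sample interval (Kenward-Roger, Satterthwaite, or t on between-cluster degrees of freedom: 6, or 5 if a site-level stratum term is added); or
- a two-stage cluster-level analysis: patient-level covariate regression without arm, then a t interval on the eight cluster mean residuals, on the same degrees of freedom.

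Apply the chosen method whether or not the between-cluster variance is estimated as zero, with no data-dependent switch. If REML is chosen, state that the between-cluster degrees of freedom are kept in that case. Use the same rule for the secondary questionnaires.

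The cost is SAP wording and a few lines of R; data collection does not change. If the default would have been a normal multiplier, intervals become up to about 25% wider: a half-width of about 0.52-0.55 SD instead of 0.42-0.44 SD at ICC 0.05.
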